As of 28 October 2013, across all subjects in all dose cohorts, the median number of treatment cycles was 4.1 cycles, with 42% of subjects continuing on treatment. Subjects who received 25 mg BID had a median time on treatment of 4.7 cycles.

Subjects with iNHL (n=32) had a median 8.5 cycles of treatment (range 0.1 to 22.7 cycles) and subjects dosed with 25 mg BID had a median of 9.8 cycles of treatment (range: 0.1 to 20.7 cycles).

In all subjects across all dose cohorts, treatment-emergent adverse events (TEAEs) have occurred in 180 (93%) subjects, including 56 subjects (92%) in the 25 mg BID dose group. The most common TEAEs ($\geq 20\%$) in all dose groups combined included fatigue (32%), ALT or AST increased (combined, 32%), diarrhea (27%), pyrexia (25%), nausea (24%), cough (22%) and neutropenia (20%). Related Grade ≥ 3 TEAEs occurred in 102 subjects (53%). The most common related Grade ≥ 3 TEAEs ($\geq 5\%$) included ALT or AST increased (combined, 16%), neutropenia (13%) and neutrophil count decreased (5%).

Across all 32 iNHL subjects, TEAEs have occurred in 31 (97%) subjects. The most common TEAEs ($\geq 20\%$) in all dose groups combined included: ALT or AST increased (combined, 53%), pyrexia (41%), rash (combined terms, 41%), fatigue (34%), diarrhea (34%), nausea (34%), neutropenia (31%) and cough (31%). Related Grade ≥ 3 TEAEs occurred in 22 subjects (69%). The most common related Grade ≥ 3 TEAEs ($\geq 5\%$) included: ALT or AST increased (combined,

Protocol IPI-145-06**Verastem, Inc.****IPI-145**

34%), neutropenia (25%), diarrhea (16%), anemia (9%), febrile neutropenia (9%), neutrophil count decreased (6%) and pneumonitis (6%).

In iNHL subjects in the 25 mg BID group, TEAEs have occurred in 15 subjects (100%). The most common TEAEs ($\geq 20\%$) included: ALT or AST increased (combined, 53%), nausea (40%), rash (combined terms, 27%), vomiting (27%), diarrhea (27%), neutropenia (27%), pyrexia (20%), fatigue (20%) and cough (20%). Related Grade ≥ 3 TEAEs occurred in 11 (73%) of iNHL subjects in the 25 mg BID group. The most common related Grade ≥ 3 TEAEs ($\geq 5\%$) included: ALT or AST increased (combined, 40%).

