4.2 DOSE INTERRUPTION/HOLD/MODIFICATION GUIDELINES

Subjects will be monitored continuously for toxicity while on study treatment. Toxicity will be assessed using the National Cancer Institute Common Terminology Criteria for Adverse Events (NCI-CTCAE) Version 4.03. If a subject has an adverse event at least possibly related to study drug, then dose interruptions/holds with possible modifications should be made according to [Table 6](#) below. Deviations from these guidelines may occur based on the clinical judgment of the Investigator with notification to the Medical Monitor/Sponsor. There should be no attempt to make up for missed doses.

Table 6: Dose Interruption/Hold/Modifications for IPI-145-Related Toxicities

IPI-145-related Toxicities ^{a, b}	Dose Interruption/Hold/Modification/Recommendation for IPI-145 ^c
Non-hematologic: Grade 2 or higher Pneumonitis/Pneumonia Or Grade 3 or higher all other Nonhematologic	First occurrence: Withhold until return to \leq Grade 1 or baseline level; re-challenge therapy at original dose level.
Hematologic: Grade 3 or higher febrile neutropenia Or New Grade 4 neutropenia >7 days duration Or Grade 3 or higher thrombocytopenia with Grade ≥ 2 hemorrhage Or New Grade 4 thrombocytopenia of any duration requiring transfusion support.	Second occurrence of same AE: Withhold until return to \leq Grade 1 or baseline level; re-initiate therapy at one dose level lower from current dose. Third occurrence of same AE: Withhold until return to \leq Grade 1 or baseline level; re-initiate therapy at one dose level lower from current dose. Fourth occurrence of same AE: Discontinue subject from study drug

Recommendations for implementation of dose interruption

Immediate hold for Grade 4 or higher nonhematologic toxicities and Grade 3 or higher febrile neutropenia
For all other events, reduce from BID dosing to QD for two days, then hold

- a. IPI-145 Related = possible, probable, or definite relationship to IPI-145 as defined in [Section 8.2.1](#).
- b. Toxicity grades are defined per CTCAE Version 4.03. Note if parameter is not defined by CTCAE, then AE grading criteria ([Section 8.2.1](#)) should be utilized.
- c. Refer to [Table 7](#) for IPI-145 dose levels.

Treatment Interruption for Nonhematologic Toxicity

Treatment with IPI-145 should be interrupted for the following nonhematologic toxicities:

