- Grade 2 or higher pneumonitis/pneumonia, defined as symptomatic and requiring medical intervention, including oral antimicrobials and/or steroids
 - Subjects who develop new pulmonary symptoms (e.g. cough, shortness of breath, dyspnea on exertion) or new radiographic findings should have IPI-145 held and receive empiric antimicrobial coverage while undergoing evaluation. Corticosteroids for symptomatic treatment of pneumonitis is recommended (and allowed per protocol). Restarting treatment with IPI-145 is allowed after complete resolution of symptoms.
- Grade 3 or higher other nonhematologic toxicity including the following:

- Infections: Subjects who develop infections requiring IV antibiotics/antifungals/anti-virals should have IPI-145 held until infection resolves (subject may restart IPI-145 while completing a course of oral therapy). Prophylaxis to prevent recurrence/opportunistic infections will not preclude the subject from restarting treatment.
- Hepatic events: Subjects who develop Grade 3 or higher transaminase (ALT/AST) elevations with or without clinical symptoms should have IPI-145 held until return to \leq Grade 1. Additional work-up to evaluate viral infection/reactivation, exposure to environmental toxins (e.g. alcohol/con-meds), or other causes is recommended before restarting treatment with IPI-145.
- Gastrointestinal: Subjects who develop Grade 3 or higher nausea, vomiting or diarrhea despite optimal treatment should have IPI-145 held until resolution of symptoms. Evaluation of concomitant medications, gastrointestinal infections or inflammatory bowel (via endoscopy and biopsy) should be considered with persistent diarrhea or recurrence with restarting IPI-145. Corticosteroids (budesonide) with taper are allowed if colitis is suspected/cannot be ruled out.
- Skin rash: Subjects who develop Grade 3 or higher skin rashes should have IPI-145 held until return to \leq Grade 1. In the setting of new Grade 1-2 skin rash early intervention is recommended to ameliorate risk of worsening symptoms. Evaluation of concomitant medications, environmental exposure, infections or other contributing factors is recommended.

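### Protocol Section 4.2 gives two hold triggers for related Grade 3 or higher nausea, vomiting or diarrhea: one unconditional, one conditional on optimal treatment

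*Protocol*

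**What the plan says.** All the hold rules at issue are in Protocol Section 4.2.

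- **Direction to the table.** The opening paragraph states: "If a subject has an adverse event at least possibly related to study drug, then dose interruptions/holds with possible modifications should be made", and names Table 6 as the rule to follow.
- **Table 6.** Apart from pneumonitis/pneumonia, which has its own threshold, the nonhematologic trigger is "Grade 3 or higher all other Nonhematologic". Nothing is said about prior or concurrent supportive treatment. At the first occurrence drug is withheld until "Grade 1 or baseline level; re-challenge therapy at original dose level". The second and third occurrences of the same event each cost one dose level, and the fourth ends treatment.
- **Narrative list, lead-in and parent bullet.** The list opens with "Treatment with IPI-145 should be interrupted for the following nonhematologic toxicities". The bullet above the gastrointestinal item reads "Grade 3 or higher other nonhematologic toxicity including the following". Neither carries a condition.
- **Narrative list, gastrointestinal item.** Subjects who develop "Grade 3 or higher nausea, vomiting or diarrhea despite optimal treatment should have IPI-145 held until resolution of symptoms".

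The section also lets investigators depart from the guidelines on clinical judgment if they notify the Medical Monitor or sponsor. Section 6.3.8.1 leaves antiemetics and antidiarrheals to the investigator's discretion and ASCO guidelines. It does not define optimal treatment.

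**The concern.** The trigger for starting a hold is written with a condition in one place and without it in two others. The question is who is held, not how a hold is carried out or when it ends.

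The difference carries forward because Table 6 counts occurrences of the same event. If one site treats a Grade 3 diarrhea that settles on antidiarrheals as a first occurrence and another does not, the next episode leads to different actions at the two sites. About 100 sites are planned (Protocol Section 4).

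The SAP summarizes dose interruptions, dose reductions and relative dose intensity (Section 7.1.6), and tabulates treatment-emergent events that led to interruption, reduction or discontinuation (Section 7.3.1). If sites follow different passages, those tables combine two rules and cannot be read as the result of either.

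**Working it through.** The plan states no figure to reproduce. The check sets the passages side by side, then asks what the documents allow one to say about size.

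**1. Same event, two passages.** Take a related Grade 3 diarrhea that is not yet treated, or that is responding to antidiarrheals.

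| Text in Section 4.2 | Condition on treatment | Trigger met? |
|---|---|---|
| Table 6, nonhematologic row | none | yes |
| Parent bullet of the narrative list | none | yes |
| Gastrointestinal item | event develops despite optimal treatment | no, on the natural reading |

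The narrative is thus at odds with itself as well as with the table. Table 6's implementation note does not supply the missing condition. A Grade 3 gastrointestinal event is not on the immediate-hold list, so it falls under "For all other events, reduce from BID dosing to QD for two days, then hold", which still ends in a hold.

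**2. Is the qualifier idle?** The hepatic (transaminase) and skin-rash items in the same list trigger at Grade 3 or higher with no treatment condition, in line with Table 6. The gastrointestinal item adds one. Either it changes who is held, and so conflicts with Table 6, or it does nothing.

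**3. Effect through the occurrence count.** Suppose a subject has four separate related Grade 3 diarrhea episodes, each responding to treatment, with no re-escalation in between (dose levels from Table 7).

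| Episode | Table 6 | Gastrointestinal item alone |
|---|---|---|
| 1 | hold, restart at 25 mg BID | no hold called for |
| 2 | hold, restart at 15 mg BID | no hold called for |
| 3 | hold, restart at 10 mg BID | no hold called for |
| 4 | discontinue | no hold called for |

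This is the extreme case. It shows how far the two texts can diverge, not how often they will.

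**4. Scope.** The gastrointestinal item names nausea, vomiting and diarrhea. Other Grade 3 or higher gastrointestinal toxicities meet no qualifier, so they show no mismatch.

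**5. Size.** Protocol Section 1.3.3.2 lists related Grade 3 or higher events in the 32 iNHL subjects of Study IPI-145-02, including "34%), neutropenia (25%), diarrhea (16%), anemia (9" (the first percentage is ALT or AST increased).

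- Diarrhea: 16% of 32 is 5 subjects (5/32 = 15.6%). The exact (Clopper-Pearson) 95% interval is 5.3% to 32.8%.
- Dose mix of the 32: 15 mg BID, 1; 25 mg BID, 15; 50 mg BID, 1; 75 mg BID, 15. So 16 of 32 received more than this trial's starting dose of 25 mg BID.
- At 25 mg BID (n = 15), the related Grade 3 or higher list in the available text names only ALT or AST increased, at 40% (0.40 × 15 = 6 subjects), although 11 subjects had such an event. One subject is 1/15 = 6.7%, above the 5% listing cut-off, so the list does not account for everyone and cannot show that diarrhea was absent. Any-grade diarrhea, whatever the cause, was 27%, or 4 of 15. Related Grade 3 or higher diarrhea could therefore be anywhere from 0 to 4 of 15.
- The share of such events that respond to treatment, which is what separates the two triggers, is not given anywhere.

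**The case against.** The strongest defense is structural. The gastrointestinal item sits under an unconditional parent bullet and a lead-in calling for interruption, and the section's opening directs related events to Table 6. On that view the sub-items add management detail and exempt nobody. The item does not say that a hold applies only to events persisting on treatment, and no text says a treated Grade 3 event is not held. The rules are also called guidelines, and departures are allowed with notification.

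Part of this stands. A reader might infer that the item expressly exempts Grade 3 events that respond to treatment; that is the natural reading of the qualifier, not its wording. But the defense leaves the qualifier with no function. The direction to Table 6 is not a precedence rule over the narrative of its own section. The deviation clause does not help either, because a site cannot tell which course is the deviation that needs notification.

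A second tempting step is to project 5/32 onto this trial: 120 × 5/32 = 18.75, about 19 subjects, or about 6 to 39 using the interval (120 × 0.053 to 120 × 0.328), and then to assume some fraction responds. The documents do not support this as an estimate. The rate pools doses, half of the subjects having received more than 25 mg BID, and any response fraction would be invented. Nor would nausea and vomiting clearly add much: neither appears in the list of related Grade 3 or higher events seen in at least 5% of the 32 subjects.

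Finally, the study is single-arm and the affected SAP outputs are descriptive. That is correct, and it limits the consequence.

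**Conclusion.** The inconsistency is real and confined to related Grade 3 or higher nausea, vomiting and diarrhea. The conclusion rests on reading the qualifier as a condition for the hold, and on the absence of any text saying which statement governs. It does not rest on an event rate.

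The number of subjects affected cannot be estimated from the documents. Differences between sites in holds, reductions, discontinuations and relative dose intensity are possible consequences, not demonstrated ones. A reader might infer that the primary analysis is compromised; nothing in the documents shows an effect on the response-rate test. This is an inconsistency in the text that should be corrected because it bears on how patients are handled and on how the exposure and safety tables are read. No view is taken on which trigger is clinically right.

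**What to change.** Reconcile Table 6, the parent bullet and the gastrointestinal item so that all three state the same hold trigger for nausea, vomiting and diarrhea, and make clear how these events relate to the Table 6 occurrence count. The sponsor's clinical team decides the content.

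The cost is about a sentence in a protocol amendment or clarification letter. It needs no new data collection.

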- Cardiac: Subjects who develop new Grade 3 or higher cardiac events should have IPI-145 held until resolution of symptoms. This includes new Grade 3 QTcF prolongation only if >20 ms increase from Baseline. A new Grade 3 QTcF prolongation (>20 ms from baseline) requires triplicate ECGs with the average measurement used and the use of Fridericia's correction method (QTcF). For subjects with a right or left BBB, a new Grade 3 QTc prolongation is defined as an increase in QTcF of >100 ms from the pre-dose ECG to any post dose ECG as the QRS interval is prolonged at Baseline (by approximately 40 ms) in subjects with a BBB

Subjects requiring treatment interruption should be re-evaluated at least weekly until the toxicity improves to \leq Grade 1 or returns to Baseline level. IPI-145 dose will be restarted at doses described in [Table 7](#).

Treatment Interruption for Hematologic Toxicity

Worsening or transient Grade 3 or higher neutropenia, anemia, and/or thrombocytopenia caused by the subject's existing disease or by IPI-145 are to be expected. Blood counts should be monitored as described in the protocol with the frequency increased as clinically indicated in the setting of new or worsening Grade 3 or higher cytopenias. IPI-145 dosing may be interrupted at any time, at the discretion of the treating physician.

Treatment with IPI-145 should be interrupted for the following symptomatic hematologic toxicities:

- Grade 3 or higher febrile neutropenia
- Grade 3 or higher thrombocytopenia associated with Grade 2 or higher hemorrhage

**Protocol IPI-145-06
IPI-145****Verastem, Inc.**

The subject should be re-evaluated at least weekly until the toxicity improves to \leq Grade 1 or returns to Baseline.

A dose may be withheld up to 42 days for toxicity. Doses withheld for >42 days due to treatment-related toxicity will result in permanent discontinuation from treatment. Any subject who requires reduction to less than 10 mg BID due to repeat occurrence of the same treatment-related toxicity will be permanently discontinued from treatment. Any subject who requires reduction to less than 5 mg BID for different treatment-related toxicities will be permanently discontinued from study treatment. Dose levels are shown in [Table 7](#).

Table 7: IPI-145 Dosing Levels

Dose Level	Dose (mg)
1	25 BID
-1	15 BID
-2	10 BID
-3	5 BID

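### Protocol Section 4.2 directs a hold for four hematologic toxicities in Table 6 but for only two in its text, and does not say which governs

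*Protocol*

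**What the plan says.** Section 4.2 of the protocol opens with a general instruction. If an adverse event is at least possibly related to study drug, "then dose interruptions/holds with possible modifications should be made according to" Table 6.

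The hematologic part of Table 6 has four triggers:

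1. "Hematologic: Grade 3 or higher febrile neutropenia"
2. "New Grade 4 neutropenia >7 days duration"
3. "Grade 3 or higher thrombocytopenia with Grade" 2 or higher hemorrhage
4. "New Grade 4 thrombocytopenia of any duration requiring transfusion support"

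The table attaches a ladder to repeat events. After the first occurrence the drug is held and resumed at the original dose. After the second and third it is held and resumed one level lower. The last step is "Fourth occurrence of same AE: Discontinue subject from study drug".

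Later in the same section, under the heading Treatment Interruption for Hematologic Toxicity, the text says that worsening or transient Grade 3 or higher neutropenia, anemia or thrombocytopenia "caused by the subject's existing disease or by IPI-145 are to be expected". It asks for closer blood-count monitoring where indicated and lets the treating physician interrupt dosing at any time. It then states "Treatment with IPI-145 should be interrupted for the following symptomatic hematologic toxicities" and gives two bullets, which match triggers 1 and 3.

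Section 4.2 also lets the investigator depart from the guidelines on clinical judgment, with notification to the Medical Monitor or sponsor.

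**The concern.** The text list is the only place in the running prose that says when a hematologic toxicity should lead to interruption, and it is half as long as the table. It sits next to a statement that severe cytopenias are expected and that other interruptions are discretionary. A site working from the text could leave a subject on drug where a site working from Table 6 would hold.

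More than one hold is at stake. Table 6 counts occurrences, so an event that is not treated as a trigger also does not move the subject toward a lower dose or discontinuation. With about 120 subjects at about 100 sites (Section 4), the average is 120/100 = 1.2 subjects per site, so many investigators would each settle the question alone.

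**Working it through.** No sample size, power or error rate bears on this point, and the plan gives no figure to reproduce. The check sets the two parts of Section 4.2 side by side for IPI-145-related events, since Table 6 is limited to those.

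| Hematologic event | Table 6 | Text list |
|---|---|---|
| Febrile neutropenia, Grade 3 or higher | Hold, counted | Should be interrupted |
| New Grade 4 neutropenia, more than 7 days | Hold, counted | Not named; discretionary |
| Thrombocytopenia Grade 3 or higher with hemorrhage Grade 2 or higher | Hold, counted | Should be interrupted |
| New Grade 4 thrombocytopenia needing transfusion | Hold, counted | Not named; discretionary |

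**Count.** There are four triggers in the table and two in the text. Both text items are in the table, so the difference is two.

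**Narrowing the two.** Prolonged Grade 4 neutropenia with fever falls under the febrile neutropenia item, which both places name. Transfused Grade 4 thrombocytopenia with Grade 2 or higher hemorrhage falls under the hemorrhage item, which both also name. The mismatch is therefore confined to:

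- new Grade 4 neutropenia beyond 7 days without fever;
- new Grade 4 thrombocytopenia needing transfusion, without Grade 2 or higher hemorrhage.

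**Nature of the difference.** For these events Table 6 directs a hold, subject to the deviation clause. The text names no directed hold and leaves the matter to the physician.

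**Precedence.** The opening sentence sends related events to Table 6. Nothing in the hematologic text refers back to the table's triggers, calls the list a subset, or says which prevails.

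**Comparison within the section.** The matching nonhematologic text repeats both nonhematologic categories of Table 6: pneumonitis/pneumonia at Grade 2 or higher, and other toxicity at Grade 3 or higher. Only the hematologic list is shorter than the table.

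**Where the difference would surface.**

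- SAP Section 7.1.6 summarizes dose reductions and interruptions, including those due to adverse events.
- SAP Section 7.3.1 tabulates adverse events leading to interruption, reduction and discontinuation.
- Protocol Section 8.2.2.4 makes a study-drug adjustment one of several grounds for reporting an abnormal laboratory value as an adverse event. The reading chosen may therefore affect whether a low count without symptoms is recorded as one.
- The primary test in SAP Section 7.2.1.1 (exact binomial, null of 30% or less, all treated subjects in the denominator) is specified without reference to these rules and does not change.

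**The case against.** The strongest defense is that the two places can be followed together. The section opens by sending related events to Table 6. The text list does not claim to be complete, forbids no hold, and is limited to symptomatic toxicities, whereas the two absent triggers are defined by count, duration or transfusion. The nonhematologic lead-in carries no such limit, which weakens the argument that the hematologic list should also be read as complete. The statement about expected cytopenias covers worsening or transient ones and includes those due to underlying disease. It can stand beside a hold for new and prolonged events.

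Much of this stands, and it rules out a stronger reading. A reader might infer that such a subject must be held under the table and needs only closer monitoring under the text. The documents do not support that. Section 4.2 is a set of guidelines worded with should and open to deviation, and the text expressly allows interruption at any time.

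The defense does not remove the mismatch. That Table 6 controls has to be inferred. The qualifier symptomatic can equally be read as the principle that separates directed holds from discretionary ones. The deviation clause is little protection, because a site following the text would not know that it was deviating and would have no reason to notify anyone.

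**Conclusion.** Section 4.2 is internally inconsistent on hematologic interruption. For the two narrowed events, Table 6 directs a hold and counts the occurrence, the text leaves interruption to discretion, and no sentence says which controls. Sites may therefore differ in holding and counting, with effects on safety management and on descriptive dose-modification summaries. The test of overall response rate is unaffected. This is a wording inconsistency in a safety rule, and it deserves correction because the rule drives reductions and discontinuation.

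The number of subjects affected cannot be estimated from the documents. A reader might try the Phase 1 iNHL figures in Section 1.3.3.2 (n=32, all doses), where related Grade 3 or higher neutropenia was 25% and febrile neutropenia 9%. That gives 0.25 × 120 = 30 and 0.09 × 120 = 10.8, hence about 19 subjects in dispute. The figure does not measure the event, for three reasons:

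- It counts Grade 3 or higher neutropenia of any duration, not new Grade 4 beyond 7 days.
- 15 of the 32 subjects received 75 mg BID, three times this trial's 25 mg BID starting dose.
- It assumes that febrile cases are a subset of the neutropenia cases, although the two are listed as separate terms.

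No rate is given for transfused Grade 4 thrombocytopenia either.

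The conclusion rests on reading the occurrence ladder in Table 6 as applying to its hematologic as well as its nonhematologic triggers.

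**What to change.** Reconcile Table 6 with the text under Treatment Interruption for Hematologic Toxicity in one of two ways:

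- make both name the same hematologic triggers; or
- keep the shorter list, and state in the text that it is a subset and which place controls.

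In either case, make clear that the same set of events counts as an occurrence for the reduction and discontinuation ladder. The sponsor's clinical team decides which set stands; this point takes no position on that.

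The cost is an edit to one bullet list, one table cell or one sentence in a protocol amendment. It needs no new assessments and no change to the SAP.
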